Tests of the association between DHA levels during pregnancy and offspring outcomes provide further evidence for the hypothesis that DHA modulates the effects of prenatal stress. Using experimental rodent models, deficient levels of DHA during pregnancy result in offspring deficits in learning, such as habituation to novelty and latency to reach learning criteria (Moriguchi, Sheaff-Griener & Salem, 2000), prolonged corticosterone response to restraint stress and longer periods of immobility during the Porsolt forced swim test (Chen & Su, 2012), and less exploration of environmental stimuli (Palsdottir, et al., 2012). Takeuchi and colleagues (2003) demonstrated that pups of DHA deficient dams spent less time in the open arms of a plus maze (indicative of higher stress levels) than the offspring of the normally fed animals. A one-week period of DHA supplementation to the diet of the pups, however, resulted in significant increases in time spent in the open arms. In one of the most compelling experimental studies to date, Feng and colleagues (2012) demonstrated in a rodent model that DHA administration during pregnancy attenuated the effects of prenatal stress on offspring hippocampal functioning including observed learning and memory, apoptosis and mitochondrial metabolism. In another rodent model, offspring of dams who received DHA and EPA supplementation beginning in pre-conception and continuing through lactation showed an attenuation of the behavioral and cognitive deficits typically elicited by olfactory bulbectomy, a manipulation that results in a phenotype consistent with depression in the human (Pudell et al., 2014).

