The extant data support the hypotheses that prenatal stress confers neurodevelopmental risks in the offspring; that DHA supports a more modulated response to stress; that DHA levels during pregnancy are associated with neurodevelopment in the offspring; and that supplementing the diet of mothers with DHA during pregnancy can lead to more optimal child outcomes. Importantly, research using animal models show that DHA administration during pregnancy attenuates the effects of prenatal stress on offspring neurodevelopment. Although both the animal and human literature supports the hypothesis that fatty acid supplementation may be most beneficial for pregnancy women exposed to high levels of stress, to date no investigator has tested whether supplementing the diets of women who are experiencing acute and/or chronic stress will improve maternal health and reduce the suboptimal development outcomes in humans.

In the U.S., higher levels of acute and chronic stress are found among families living in low-income environments than among families living in other income environments: neighborhood disorder, lack of safety and exposure to violence are all significantly higher in areas with lower per capita income (Evans, 2003; Ewart & Shuchdat, 2002). African Americans live in poverty at a disproportionately high rate, with more than a quarter of African Americans living in poverty (DeNavas-Walt & Proctor, 2014). Pregnant women living in poverty are at higher risk for poor nutrition during pregnancy (Noble et al., 2007; Fowles & Gabrielson, 2005) and are more likely to experience pregnancy complications (Giscombé & Lobel, 2005). This is especially the case for African American women living in urban low-income environments (Kent et al., 2013). Greater exposure to psychosocial stress during the prenatal period has been hypothesized be a primary mechanism by which poverty confers risk for physical and mental health disorders to the offspring (Reynolds et al., 2013; Robinson et al., 2008).

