Infant gender, mothers' postpartum stress, depression, and anxiety levels will be compared between those received DHA supplements during pregnancy and those who did not using ANOVA. If significant differences are found, then these factors will also be controlled for in the analyses. If time of collection is associated with cortisol values, then this will also be controlled for in the analyses. However, since a circadian rhythm is not firmly established prior to the age of 6 months, we do not expect to have to control for time of day at 1 and 4 months.

Power Calculations for Hypothesis 2. Based on published data on maternal report of difficult temperament in infants using the ICQ (Keenan et al., 1998), the estimated SD for the ICQ in the proposed study is 7.8. With 108 participants in the supplement group and 54 in the placebo group, there will be 80% power to detect a difference in the ICQ of 3.7 between the two groups at a given visit, using a two-sided test at the 0.05 significance level.

The SD for 30–minute post-test cortisol levels in response to the FFSF paradigm was reported as 0.4 μ g/dL (Hayley & Stansbury, 2003). If we assume a similar amount of variability in peak responses to the FFSF, with 108 participants in the supplement group and 54 in the placebo group, there will be 80% power to detect a difference of 0.19 μ g/dL between the two groups, using a two-sided test at the 0.05 significance level.

[figure not shown]
In addition, there will be approximately 90% power to detect a difference in birth weights of the same magnitude as that observed in our preliminary study (3174+/-480 vs. 2889+/-549 g), using a two-sided test at the 0.05 significance level.

Hypothesis 3. The association between DHA supplementation during pregnancy and infant outcomes will be partially mediated by reductions in maternal perceived stress, stress reactivity during pregnancy.

Mediation will be tested using the Baron and Kenny approach (Baron & Kenny, 1986) with the following general model:

$$g(E(Y_i)) = \alpha + \beta M_i + \omega T_i + \lambda Z_i$$

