 Y_i is an outcome for infant i, g is a link function (e.g. logistic or identity), M_i is a maternal stress measure at the final prenatal visit for the mother of infant i, T_i is treatment group (e.g. 0=placebo vs. 1=active; average DHA level in the blood across prenatal visits), and Z_i is a vector of additional covariates such as infant gender, mothers' postpartum stress, depression, or anxiety. The change in ω due to adding maternal stress to the model provides an estimate of the proportion of the treatment effect due to this factor; if ω is still significant but the magnitude is reduced, this would provide evidence for partial mediation. For infant outcomes collected at multiple visits, the initial approach will be to use data from the last visit, but longitudinal approaches may be considered depending on the results from the initial analyses. To provide greater power for detecting such effects, bootstrapped confidence intervals will be examined. Since multiple measures of maternal stress will be collected, the model may be extended to permit multiple mediators.

Power Calculations for Hypothesis 3. Based on simulation results presented in Fritz et al. and the SAS program provided at http://ripl.faculty.asu.edu/wp-content/uploads/2013/02/baronkenny3.txt, 162 subjects will provide sufficient power (>80%) to detect the following effects based on Cohen's criteria. As shown in Figure 6 and Table 2, the study with 162 subjects will be sufficiently powered (>80%) to detect medium effects for the α and β paths and small effects for the direct effect (scenario 1), or small-medium effects for the α and β paths and medium effects for the direct effect (scenario 2), which is plausible based on the effects found in the preliminary study.

Table 2: Overview of power for mediation hypothesis

	α path	β path	Direct effect	
scenario 1	medium	medium	small	
scenario 2	small-medium	small-medium	medium	

Missing data. Missing data is not expected to be a major issue based on retention rates from the preliminary study. The last observation carried forward (LOCF) approach for missing data will be employed. Sensitivity analyses using complete-cases only will also be performed and the results using the two approaches compared. Related to this, treatment non-compliers will be included in the primary analysis based on the intent-to-treat (ITT) principle.

Timeline for participant visits

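### The Hypothesis 3 mediation model allows one stress slope for both arms, so if DHA also weakens the effect of stress on the infant, the reported stress share is a blend of two slopes and that protection falls into ω

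*Combined protocol and SAP*

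**What the plan says.** Hypothesis 3 states that the DHA effect on infant outcomes is "partially mediated by reductions in maternal perceived stress, stress reactivity during pregnancy". The model is "g(E(Y_i)) = \alpha + \beta M_i + \omega T_i + \lambda Z_i", where "M_i is a maternal stress measure at the final prenatal visit for the mother of infant i" and "Z_i is a vector of additional covariates such as infant gender, mothers' postpartum stress, depression, or anxiety". T is the randomised arm or, alternatively, the average blood DHA level. There is no product of T and M. The extensions foreseen are longitudinal outcomes and more than one mediator. The analyses for Hypotheses 1 and 2 include group, group-by-time and group-by-visit terms, but none by stress level.

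The result is read as follows: "The change in ω due to adding maternal stress to the model provides an estimate of the proportion of the treatment effect" attributable to stress, and "if ω is still significant but the magnitude is reduced, this would provide evidence for partial mediation".

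The rationale has two strands. In one, DHA lowers the mother's own stress and reactivity. In the other, DHA alters what stress does to the child. The Significance section on DHA levels and offspring outcomes says that such studies "provide further evidence for the hypothesis that DHA modulates the effects of prenatal stress", and the Innovation section says that "DHA administration during pregnancy attenuates the effects of prenatal stress on offspring neurodevelopment". Both sections add that protection may be greatest where stress is high.

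**The concern.** The second strand can be read as effect modification: at the same level of maternal stress, the infant is harmed less under DHA. In model terms, the slope of Y on M would be smaller in the active arm. A model with one β cannot represent that. It averages the two slopes, multiplies the average by the arm difference in stress, and leaves everything else in ω.

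Hypothesis 3 exists to attribute the effect. If the slopes differ, the reported share belongs to neither arm, and readers may take a large ω as protection that does not depend on stress. The plan would then offer no estimate of the stress-dependent protection that its rationale raises.

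**Working it through.** **The plan's own figure.** The Hypothesis 3 power statement is above 80% with 162 subjects, with effect sizes given only as verbal labels. With assumed standardised paths (α, β, direct) of 0.39/0.39/0.14 and 0.26/0.26/0.39, simulation gives about 93% and 80%, in line with the claim. With 0.3/0.3/0.1 and 0.2/0.2/0.3 it gives about 60% and 48%. The statement concerns the planned model and says nothing about an interaction.

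**Inputs from the documents.** Arms of 108 and 54. Pilot perceived stress at 30 weeks of 27.5 (SD 3.4) on active and 29.3 (SD 3.1) on placebo, both from the Hypothesis 1 power section. Pooled SD = √[(107×3.4² + 53×3.1²)/160] = 3.30, so the shift is 1.8/3.30 = 0.545 SD.

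**Assumptions not in the documents.** A continuous outcome scored so that higher is worse; T = arm; no covariates; a placebo slope b₀ = 0.39 per SD of stress; a DHA slope b₁ of 0 or 0.195; and placebo mean stress k = 1 SD above the level at which stress has no effect. Within each arm Y = b·M + noise, so DHA acts only through the level of stress or its slope.

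**Formulas.**
- Total effect = b₁(k − 0.545) − b₀k
- Pooled slope with equal SDs ≈ (54·b₀ + 108·b₁)/162
- Planned indirect effect = −0.545 × pooled slope; ω = total − planned indirect effect
- Natural indirect effect = −0.545·b₀ (placebo slope) or −0.545·b₁ (DHA slope)

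**Results at k = 1.**

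| | Slope abolished (b₁ = 0) | Slope halved (b₁ = 0.195) |
|---|---|---|
| Total | −0.390 | 0.195×0.455 − 0.39 = −0.301 |
| Pooled slope | 0.130 | 0.260 |
| Planned indirect | −0.071 | −0.142 |
| ω | −0.319 | −0.160 |
| Planned share | 18% | 47% |
| Share at placebo slope | 0.2126/0.390 = 55% | 0.2126/0.301 = 71% |
| Share at DHA slope | 0% | 0.1063/0.301 = 35% |

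At k = 2 the planned shares are 9% (against 27% and 0%) and 29% (against 43% and 21%). With equal slopes every version gives 100%, as it should.

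**Same check on the pilot scale.** With the pilot SDs, the weight on the DHA slope is 108×3.4²/(108×3.4² + 54×3.1²) = 0.706, leaving 0.294 on placebo. Take a no-effect level of 26.2, one placebo SD below the placebo mean, and count in units of the placebo slope. Slope abolished: total 3.1, planned indirect 1.8×0.294 = 0.53, share 17%. Slope halved: total 2.45, planned indirect 1.8×0.647 = 1.16, share 48%.

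**No shift in mean stress.** If DHA only flattens the slope, the planned indirect effect is zero and the whole benefit stays in ω.

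**Counter-case.** Suppose DHA weakens the step from stress exposure to maternal reactivity, and reactivity acts on the infant with one slope in both arms. With M = reactivity the planned model credits 99.7% of the effect. With M = exposure or perceived stress it credits about 0%.

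**Power for a T×M term at 108/54.** With an assumed stress–outcome correlation of 0.3 in placebo: 15–16% if the slope is halved, 47% if abolished. With 0.5: about 40% and 92–93%.

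**Cost in precision when slopes are equal.** To first order, with unit residual SD, Var(indirect) = a²Var(b) + b²Var(a), with a = 0.545, b = 0.39 and Var(a) = 1/108 + 1/54 = 0.0278. Taking Var(b) as about 1/160 (pooled), 1/106 (DHA) and 1/52 (placebo) gives SDs of 0.078, 0.084 and 0.100. Simulation likewise puts the increase over the planned model at about 8% (DHA slope) and 27% (placebo slope).

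**The case against.** The strongest reply is that Hypothesis 3 asks about mediation by reductions in stress, and a flatter slope at unchanged stress is not a reduction. This stands. A reader might take 100% as the true share in these scenarios, because all benefit involves stress by construction, and conclude that the plan gives a wrong answer. The documents do not support that: 100% is not the quantity Hypothesis 3 names. The planned share also always lies between the two natural indirect shares, since the pooled slope is a weighted mean, and in the abolished case the DHA-slope version credits less than the plan does.

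Second, the rationale does not entail unequal slopes on M. The animal studies imposed the stress, and weakening the effect of an imposed stressor is also what mediation through lower maternal reactivity would produce. Reactivity is a named mediator, and the causal chain in the Innovation section runs through it. So it goes too far to say that the model contradicts the rationale or is blind to protection. The loss arises mainly with perceived stress as M, or when protection acts beyond measured reactivity.

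Third, the high-stress argument is used to choose the population, not to claim moderation within the trial, and the plan never says that the remaining ω is unrelated to stress. Both are true. But the plan reads the change in ω as the share due to stress without warning what else ω may hold, and with two named mediators that can disagree as sharply as in the counter-case, it gives no rule for interpreting the disagreement.

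**Conclusion.** The point holds as a limit on interpretation and a cheap improvement, not as an error that invalidates Hypothesis 3. The additive model fits the hypothesis as worded. If the slope on the chosen mediator differs by arm, its stress share is a blend weighted about one third to placebo and two thirds to DHA, and stress-dependent protection goes into ω. At k = 1 the planned share is 18% within a range of 0% to 55% (slope abolished), or 47% within 35% to 71% (slope halved).

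These sizes depend on the assumed slopes and no-effect level, which the documents do not give, and on a linear outcome without mediator–outcome confounding. The one-third/two-thirds weighting applies when T is the arm, not when it is the blood DHA level. Only attribution is affected; the total infant effect under Hypothesis 2 is not.

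**What to change.** Keep the additive model for Hypothesis 3 as worded. Prespecify beside it g(E(Y)) = α + βM + ωT + θ(T×M) + λZ, with θ retained whatever its p-value. Report θ with its interval, and the natural direct and indirect effects evaluated under each arm, using the bootstrap intervals already planned. In this model ω is the arm effect at M = 0, so interpret the natural effects instead. Label the results as estimation, since power for θ runs from about 15% to 93% across the assumed values. Add a sentence that ω from the additive model may contain stress-dependent protection and is not to be read as unrelated to stress.

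The cost is SAP wording and one model term, with no new data. When the slopes are in fact equal, the indirect effect is less precise than in the planned model: its SD is about 8% larger at the DHA slope and 27% larger at the placebo slope.

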In addition to associations between DHA supplementation and prenatal stress, we observed significantly higher birth weights among neonates born to women receiving DHA compared to placebo controlling for gestational age (3,174 grams versus 2,889 grams, p = .018) and greater likelihood of having a 1-minute Apgar score of 9 (odds ratio = 5.99 [95% Cl = 1.25 - 28.75], p = .025, controlling for birth weight and gestational age). Finally, 13% of neonates of mother receiving DHA supplementation were born prior to 37 weeks, compared to 22% of mothers received placebo; a difference that did not reach the level of statistical significance in the pilot study, but is clinically meaningful.

In summary, the data from our preliminary study are compelling in terms of the potential impact on health disparities in maternal and infant health, a significant public health problem that is poorly understood. We now seek to expand on these preliminary findings by conducting a more rigorous assessment of prenatal DHA supplementation on maternal and infant health by increasing the number of participants to 162, beginning supplementation earlier in pregnancy, adding additional measures of maternal health and stress response during pregnancy, increasing the frequency of assessment, assessing DHA levels in red blood cells at each visit, and including multiple postnatal assessments of infant neurodevelopment. The proposed study offers an opportunity for replication and to test the impact of supplementation on infant functioning and, if effects are observed, whether they are mediated by changes in prenatal stress.

APPROACH

Participants

One hundred-sixty-eight pregnant, African American, women will be recruited from the University of Chicago obstetric clinic. Inclusion criteria will include: age between 18 and 34 years, household receipt of public assistance (e.g., Medicaid insurance) due to low-income, and low levels of DHA consumption as defined as less than two fish servings per week. Exclusion criteria are reports of known medical complications, regular use of steroid medications, alcohol, cigarettes, or illegal substances (by maternal report), use of blood thinners or anti-coagulants, use of psychotropic medications, BMI >40, and allergy to iodine and/or soy. Participants may be excluded if medical complications arise after enrollment. Neonates with significant medical complications will be maintained in the study.

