There are two reasons for our focus on African American women. First, as described above, African American women are disproportionately represented among families living in inner-city poverty and have the highest rates of suboptimal birth outcomes in the U.S. (Giscombé & Lobel, 2005). Second, there are racial differences in cortisol reactivity to

stress and pregnancy (De Santis et al., 2007; Glynn et al., 2007; Wilcox et al., 2005) and in the genes regulating cortisol (Baerwald et al., 1999). Given the scope of the proposed study and the potential to generate data that can be translated into reductions in health disparities, we chose to study African Americans only, but acknowledge that it will be important to test racial and ethnic differences in maternal and infant response to DHA supplementation during pregnancy.

Women will be randomly assigned to receive the omega-3 nutritional supplement (n = 112) or a corn and soybean oil placebo (n = 56) beginning at enrollment and up through the end of pregnancy. In the proposed design we allocate the number of participants to groups to optimize power to test the hypotheses. We expect greater variability in the independent measure (i.e. DHA level) and dependent measures (e.g., stress reactivity) in participants in the experimental group than those in the control group given anticipated differences in uptake and metabolism. Thus, we plan to enroll a higher number of participants in the experimental group than in the control group to adequately capture that variability (Cox, 1958). Participants and investigators will be blinded to the group to which they have been assigned. Treating clinicians will identify demographically eligible participants who will be contacted by research staff for further screening. Participants who meet the inclusion and exclusion criteria will then be scheduled for the baseline visit.

Participants will be reimbursed on an accelerated schedule with \$100 for their first visit and an increase in payments by \$25 for each subsequent visit, ending with a \$250 payment for the last post-partum visit. Participants will receive incentives in between visits including water bottles, tote bags, newborn t-shirts, etc. They also will be reimbursed with \$10 to cover travel costs for each visit.

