Nordic Naturals adheres to high standards on safety and purity by setting low levels of allowances for peroxides, heavy metals, dioxins, furans, and PCBs. A certificate of analysis is provided for every batch of ProDHA based on both an internal analysis and an analysis conducted by an independent laboratory.

The investigational pharmacy at the University of Chicago will use computer generated random assignment of ID numbers to active supplement or placebo in blocks of 18: 12 ID numbers will be randomized to active supplement and six to placebo. In order to maintain the double-blind, the pharmacist will divide each randomization block of 18 ID numbers into groups of three: six ID numbers were assigned to group A (placebo) and the remaining 12 will be assigned to either group B or C, both of which will receive identical doses of active supplement. This approach will allow the pharmacist to randomize on a 2:1 ratio without having the unbalanced design break the blind. Once the study is complete and the blind broken, the two groups receiving identical doses of active supplement will be combined for analyses.

Each participant will receive a 6-week supply. She will bring any unused DHA back to her next visit; pills will be double counted at that time as an additional method for monitoring compliance. At each visit she will receive the next supply. Research assistants will contact participants by phone 3 times per week to ask the time of day that supplement was taken, and data on perception of taste, and possible gastrointestinal side effects. At each laboratory visit research assistants will interview participants about diet over the past 24 hours and past two weeks to determine intake of sea fish or other DHA rich foods (e.g., flax seed).

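### The allergy exclusion names soy but not corn, the other oil in the placebo, so a woman with a known corn allergy is eligible as written (minor, precautionary)

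*Combined protocol and SAP*

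**What the plan says.** Under APPROACH, Participants, the exclusion list ends with "use of psychotropic medications, BMI >40, and allergy to iodine and/or soy". This is the only allergy criterion for the trial. The list begins with a general, undefined exclusion for medical complications that the woman reports as known.

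The same section gives the allocation and the placebo's make-up: "Women will be randomly assigned to receive the omega-3 nutritional supplement (n = 112) or a corn and soybean oil placebo (n = 56" women). The Nutritional Supplement section gives the block structure: of every 18, "12 ID numbers will be randomized to active supplement and six to placebo".

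On the route to enrollment, clinicians identify demographically suitable women, "who will be contacted by research staff for further screening". Then, "Participants who meet the inclusion and exclusion criteria will then be scheduled for the baseline visit".

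After enrollment, "Participants may be excluded if medical complications arise after enrollment". On supply, "Each participant will receive a 6-week supply", and research assistants telephone three times a week to "ask the time of day that supplement was taken, and data on perception of taste, and possible gastrointestinal side effects".

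The active product is identified by brand, by fatty-acid and vitamin E content and by purity standards. The source of its oil is not given.

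**The concern.** The plan excludes women allergic to one of the two oils named in the placebo and is silent on the other, with no reason given for the difference. A screener who applies the list literally would pass a woman who volunteers that she is allergic to corn. She could then be handed six weeks of capsules containing corn oil. Participants and investigators are blinded, so neither would know which oil she was taking.

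What is at stake is participant safety in a pregnant population, not the validity of any comparison. No endpoint, sample size, power figure or analysis depends on this wording.

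**Working it through.** The check is mainly a comparison of texts. The plan states no figure on this point that could be reproduced.

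**Step 1. Set the criterion against the placebo.**

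| Oil named in the placebo | Named in the allergy exclusion? |
|---|---|
| Soybean | Yes (soy) |
| Corn | No |

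One of two named placebo oils is covered. Iodine, the other listed allergen, is not a named placebo ingredient.

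**Step 2. Look for another rule that closes the gap.**
- The exclusion for known medical complications applies before the baseline visit. It is undefined and does not mention allergy, and a separate criterion in the same sentence deals with allergy and lists only iodine and soy. It might catch a serious allergy at a screener's discretion, but does not require it.
- Exclusion for complications arising after enrollment is optional and comes later.
- The listed topics of the telephone calls are timing, taste and gastrointestinal effects, and the calls ask about capsules already taken.
- Corn allergy is mentioned nowhere else in the document. The pilot, described under Preliminary support for hypotheses, used the same iodine-and-soy wording.

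**Step 3. Chance that an eligible corn-allergic woman receives corn oil.**
- From the block: 6/18 = 0.333.
- From the arm sizes: 56/(112 + 56) = 56/168 = 0.333.

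The two agree at 1 in 3.

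**Step 4. Scale.** Let p be the proportion of otherwise eligible women with a corn allergy. The documents do not give p, and none is assumed here. The expected number in the placebo arm is 56 × p, which reaches one woman only if p = 1/56 = 1.8%. Below that, fewer than one is expected. For each such exposure avoided, a corn criterion would exclude 168/56 = 3 women, because two of every three would have gone to the active arm. These figures count women with an allergy who are given the oil. They are not reaction counts.

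**Step 5. Effect on the plan's numbers.** The power calculations use 108 + 54 = 162 women and recruitment aims for 168. Women caught by the criterion leave before randomization, so neither figure changes if they are replaced. Replacement is not automatic: the schedule under Timeline for participant visits adds up to 6×8 + 4×6 + 2×8 + 4×6 + 6×8 = 160, already below 168.

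**The case against.** The strongest case against the point is that no hazard is shown. Nothing in the documents says that these oils carry allergenic protein. The plan does not say why soy is listed, and iodine is on the list without being a named placebo ingredient, so the list was not evidently built from the placebo's contents. Which allergens to name is a clinical judgement. This stands, and it limits the point to a precaution. It does not explain why one placebo oil is covered and the other is not.

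Second, the pilot used the same allergy wording with a corn and soybean oil placebo in 21 women. All four withdrawals are explained (miscarriage and mood changes on placebo, headaches and upset stomach on active), and none is reported as allergic. This is the only direct evidence and it is mildly reassuring. It cannot settle the matter: the text gives reasons for withdrawal, not a full account of adverse events, and does not say whether any of the 21 was allergic to corn. Even if there were truly no reactions in 21, the one-sided 95% upper limit is 1 − 0.05^(1/21) = 13%.

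Third, a reader might infer that every safeguard acts only once capsules have been taken. The documents do not support that. The exclusion for known medical complications is applied before baseline and could be used for a serious allergy. Consent pages are not in the text reviewed and may carry an ingredient warning.

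Fourth, a reader might infer that fish-allergic women are wrongly admitted as well. That depends on the active oil being from fish. The background on marine oils is general and the purity limits only fit such a source; neither establishes it for this product. No separate claim about fish is made.

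**Conclusion.** The point holds as a minor, precautionary gap in the eligibility wording. A woman with a known corn allergy is not excluded by any stated criterion that names her condition, and if enrolled she has a 1 in 3 chance of receiving corn oil. The number of such women is unknown, and no allergic harm is shown or claimed.

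The conclusion assumes that the exclusion list is complete as printed and that screeners apply it as written. A screener who reads the medical-complications exclusion broadly, or a consent form that lists the capsule contents, would narrow the gap in practice. It would be wrong to conclude that the trial is unsafe or that its results are affected; nothing in the documents supports either.

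**What to change.** Change the allergy criterion to: *allergy to iodine, soy, corn, or any other component of either study capsule*. Ask about it at the screening contact that already precedes the baseline visit. The component clause would cover fish if the active oil proves to be of fish origin, so no separate fish criterion is needed. The sponsor and clinicians should settle the final list.

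The cost is one line in the exclusion criteria and one question at an existing contact. The downside is that a few otherwise eligible women, number unknown, are screened out before randomization and must be replaced through recruitment, on a schedule that already totals 160 against a target of 168. If they are replaced, power and analyses stay as they are.
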